Is the perfusion index an accurate predictor of return of spontaneous circulation in cardiac arrest?

NCT: pending

STUDY SUMMARY

Title

Is the perfusion index an accurate predictor of return of spontaneous circulation in cardiac arrest?

Methodology

A perspective observational double blind study

Outcomes

Return of spontaneous circulation in a mixed population of out-of-hospital and in-hospital cardiac arrest

Study Duration

Estimated duration for the main protocol (e.g. from start of screening to last subject processed and finishing the study) is approximately 2.5 years

Study Center

Monocentric: Centre Hospitalier Universitaire Saint Pierre, Brussels, Belgium

Objectives

Primary Objective: To evaluate the sensibility and specificity of the perfusion index in predicting further return to spontaneous circulation

Secondary Objectives: To compare perfusion index specificity and sensibility in predicting further return to spontaneous circulation compared to end-tidal CO₂

Number of Subjects

92 non-randomized patients in one arms

Main Inclusion Criteria

Inclusion Criteria

- Male and female patients, 12-99 years old, in any distribution.
- Cardiac arrest with an indication to reanimate
- Consent and compliance with all aspects of the study protocol, methods, providing data during the cardiac arrest management

Exclusion Criteria

- Male and female patients younger than 12 years old or older than 99 years old.
- Prisoners
- Pregnant women

Study parameter

- Perfusion index during cardiac arrest

Statistical

Methodology

Primary Endpoint:

Sensibility and specificity of the perfusion index in predicting a return of spontaneous circulation (ROSC)

Secondary Endpoints:

Comparison of receiver operator curves from the perfusion index and the end-tidal CO₂ in predicting ROSC

Determination of the receiver operating characteristic curve of an index combining perfusion index with ETCO₂ and current rhythm

Tertiary Endpoints:

Sensibility and specificity of the perfusion index in predicting further arrest following an initial ROSC

Purpose:

The primary objective is to evaluate the sensibility and specificity of the perfusion index, measured during chest compressions for cardiac arrest, in predicting ROSC.

Background:

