Cardiac arrest prognostication is important in to inform the decision to cease resuscitation or, in the prehospital setting, to inform the decision on transport to hospital. Currently the only intra-arrest monitoring tools widely available with proven prognostic value are the underlying cardiac rhythm identified on electrocardiogram and end-tidal CO₂ (ETCO₂) measurement. Shockable rhythms, namely ventricular fibrillation and pulseless ventricular tachycardia, are associated with better outcomes than non-shockable rhythms such as pulseless electrical activity and asystole.

ETCO₂, so far, is considered the best tool available for prognostication during in or out-of-hospital cardiac arrest. Previous studies have examined ETCO₂ readings and trends at various times during cardiac arrest as a possible predictor of ROSC, survival to admission, and survival to hospital discharge. Nonetheless, ETCO₂ values have numerous limitations and no value alone can safely and accurately predict the chances of return to a spontaneous circulation (ROSC) or can safely inform on the futility of further reanimation. It would be therefore interesting for the clinician on the ground to be able to rely on a panel of different parameters to assess the chances of ROSC in a multimodal way.

Goals of the study:

1. To examine the association between absolute values of the perfusion index during resuscitation and ROSC.
2. To examine the association between the change in perfusion index values during resuscitation and ROSC.
3. To compare the performance of the perfusion index to ETCO₂ in predicting the chances of ROSC.
4. To study a combined index including rhythm, ETCO₂ and perfusion index achieves in predicting ROSC.
5. To study the ability of perfusion index to predict further arrests in patients further re-arrests in patients that achieved an initial ROSC

Duration of the Study:

The study is estimated to complete enrollment within 12 months from study initiation; however, enrolment will remain open until the study goal is met. The duration of this study for each subject will be a maximum of two years.

Product Description:

Perfusion index will be measured a the finger tip using a Radical 97 monitor (Masimo, Irvine, California). Masimo Signal Extraction Technology (SET[®]) pulse oximetry yields continual and simultaneous absolute values and trends.

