All subjects that will be treated by the mobile intensive care unit of CHU Saint Pierre during study period will be screened for eligibility. Subjects having regained a sufficient neurological awareness to sign an informed consent for the study will review and undergo informed consent.

This study will be listed at www.clinicaltrials.gov.

Data collection and reporting.

Data will be collected throughout the intervention up until death or hospital admission or intensive care admission whichever comes first.

Expected outcomes.

It is the sponsor's expectation that higher perfusion index and upwards trends will be associated with higher chances of ROSC during ALS. Moreover, the sponsor expectation is that lower perfusion index following ROSC will be associated with higher chances of re-arrest. Finally the sponsor expect that a combined index including PI, ETCO₂ and rhythm would overperform each of these items in terms of capacity of predicting ROSC chances.

Adverse reactions.

There is no expectation of any adverse outcomes or reactions due to a patient being monitored with a Radical 97 monitor. Any adverse reactions should be reported immediately to the principal investigator or co-investigators

Reasons for Withdrawal or Termination

A subject may be discontinued from the study at any time if the subject, the Investigator, or the Sponsor feels that it is not in the subject's best interest to continue.

The following is a list of possible reasons for study treatment discontinuation:

- Screening Failure
- Subject withdrawal of consent
- The treating clinician is not compliant with study or ERC procedures
- Adverse Event that in the opinion of the Investigator would be in the best interest of the subject to discontinue study participation
- Protocol violation requiring discontinuation
- Mechanical – technical failure of the monitor

Handling of Participant Withdrawals of Termination:

Although subjects may withdraw from the study at any time and for any reason, (or may be withdrawn according to the abovementioned pre-specified cases), subject withdrawal should be avoided as much as reasonably possible.

Premature Termination or Suspension of Study:

This study may be temporarily suspended or prematurely terminated if there is sufficient reasonable cause. Written notification, documenting the reason for study suspension or termination, will be provided by the suspending or terminating party to the Investigator, and the Sponsor.

SAMPLE SIZE JUSTIFICATION

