Sample Size Calculations

We an expected sensitivity and specificity of 90% for PI to predict ROSC, an expected prevalence of ROSC of 40%, a precision of 10% and a type I error rate of 0.05 we calculated a required sample size of 87. Including a possible dropout of 5% we calculated a final sample size of 92.

STATISTICAL ANALYSIS PLAN

Primary Endpoint

We will determine the predictive value of PI measures for ROSC. We will calculate the sensitivity and specificity at multiple different PI thresholds along with corresponding 95% confidence intervals. Overall discrimination of PI for ROSC will be presented as area under the receiver operator characteristic curve (AUC/ROC). PI values will be averaged on two minutes. Each value will be tested for its ability to predict ROSC during the following ALS cycle (2 minutes). To assess the trending ability of PI to detect ROSC we will measure the difference (ΔPI) between initial PI and PI values of the cycle preceding ROSC or the last cycle in the absence of ROSC. We will then examine the association between ΔPI and ROSC through a multivariable logistic regression while adjusting for predetermined baseline confounders such as age, initial rhythm, noflow time, bystander CPR and sex.

Secondary Endpoints

Superiority analysis of PI compared to ETCO₂ in predicting ROSC. Initial and final values of both PI and ETCO₂ will be assessed for their ability to predict ROSC. Moreover averaged values per 2 min cycle will be assessed for their ability to predict ROSC in the following cycle. The constructed ROC curves will be compared using the algorithm suggested by De Long.

Tertiary Endpoints

As a tertiary endpoint we will study the predictive value of PI to predict further re-arrest following a ROSC. Overall discrimination of PI for re-arrest will be presented as area under the receiver operator characteristic curve (AUC/ROC). PI values will be averaged on two minutes. Each value will be tested for its ability to predict a re-arrest during the following 2 minutes.

ASSESSMENT OF SAFETY

Adverse events (AE) will be monitored and collected by the study team during the monitoring phase of the study. For each AE, a detailed explanation will be obtained from the treating physician and medical record. All AEs will be recorded on the CRFs.

Definition of Adverse Event

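### The only comparison stated for the combined index is with each single item, which cannot show whether PI adds to ETCO₂ plus rhythm; also fit the two-item model as reference

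*Protocol*

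**What the plan says.** The Study Summary lists among the secondary endpoints "Determination of the receiver operating characteristic curve of an index combining perfusion index with ETCO₂ and current rhythm". The fourth item under Goals of the study reads "To study a combined index including rhythm, ETCO₂ and perfusion index achieves in predicting ROSC". Neither names a comparator.

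The one comparison in the document is under Expected outcomes, where the sponsor expects that the "combined index including PI, ETCO₂ and rhythm would overperform each of these items in terms of capacity of predicting ROSC chances".

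The Background gives two relevant statements. It says that at present "the only intra-arrest monitoring tools widely available with proven prognostic value are the underlying cardiac rhythm identified on electrocardiogram and end-tidal CO₂". It then motivates the work by the wish to "rely on a panel of different parameters to assess the chances of ROSC in a multimodal way".

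The protocol's own Statistical Analysis Plan section does not mention the index. Its ROC comparison is "Superiority analysis of PI compared to ETCO₂ in predicting ROSC", with the statement "The constructed ROC curves will be compared using the algorithm suggested by De Long". The regression of the change in PI on ROSC adjusts for age, initial rhythm, no-flow time, bystander CPR and sex. ETCO₂ is not in that list.

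**The concern.** PI is the only new item in the index; the protocol itself treats the other two as established. Two established predictors that carry different information will usually do better together than either does alone. An index that contains both can therefore beat each single item whether or not PI contributes.

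A higher AUC for the index than for each component is easily read as support for adding PI to current monitoring. If PI largely duplicates ETCO₂, that reading would be wrong. PI would look predictive on its own, the index would look better than every item, and no planned comparison would show that PI contributed nothing.

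**Working it through.** **The protocol's own figure.** With sensitivity 0.90, precision 0.10 and z = 1.96: 1.96² × 0.90 × 0.10 / 0.10² = 34.57. Dividing by the ROSC prevalence of 0.40 gives 86.4, so 87. The specificity requirement is 34.57 / 0.60 = 57.6, so 58, and sensitivity governs. With 5% dropout, 87 / 0.95 = 91.6, so 92. Both stated sizes reproduce.

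**Inputs for the check.** From the protocol: 0.40 × 87 = 34.8, so about 35 ROSC and 52 non-ROSC; and "an expected sensitivity and specificity of 90% for PI to predict ROSC". Assumed, because the protocol gives no values: ETCO₂ AUC 0.65 to 0.85; shockable rhythm from 40% vs 25% to 50% vs 20% (ROSC vs no ROSC); normal ETCO₂ and PI; logistic models; one row per patient.

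**How PI is set up.**
- Noise: PI unrelated to ROSC and to ETCO₂.
- Redundant: PI's mean shift equals the correlation times the ETCO₂ shift, so PI carries nothing beyond ETCO₂. With ETCO₂ AUC 0.76 the shift is √2 × Φ⁻¹(0.76) = 1.00 SD. At correlation 0.5 PI shifts by 0.50 SD, and its own AUC is Φ(0.50/√2) = 0.638.
- Excellent: 90%/90% means a separation of 2 × 1.2816 = 2.563 SD, an AUC of Φ(2.563/√2) = 0.965.

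**Large samples.** With ETCO₂ AUC 0.75, shockable rhythm 50% vs 15% and redundant PI at correlation 0.7, the AUCs are: ETCO₂ 0.750, rhythm 0.676, PI 0.681, ETCO₂ + rhythm 0.810, all three 0.810. The index exceeds the best single item by 0.810 − 0.750 = 0.060, and none of that comes from PI.

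**At the planned size** (ETCO₂ AUC 0.76, rhythm 50% vs 20%; share of simulated studies):

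| PI | Index beats every item (same-data AUC) | ETCO₂ + rhythm beats every item | Likelihood-ratio test for PI rejects |
|---|---|---|---|
| Redundant, AUC 0.638 | 98.5% | 97.2% | 5.6% |
| 90%/90%, AUC 0.965 | 92–98% | 0–0.1% | 100% |

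Over the whole assumed range with noise or redundant PI, the index beats every item numerically in 89–99% of studies, while the likelihood-ratio test rejects in roughly 4–7%. If beating is taken to mean De Long p < 0.05 against all three items, the share is 1–19%. It is 10–33% when rhythm is assumed stronger (40–50% vs 15%).

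**What the planned analyses already catch.**
- Noise: the lower 95% limit of PI's own AUC exceeds 0.5 in only 2–3% of studies, so the primary endpoint exposes it.
- Excellent PI: the planned De Long comparison finds PI superior to ETCO₂ in 76–100% of studies, and in 92–100% in a separate run. With a useless PI it does so in 0–0.2%.
- Redundant at correlation 0.5: the lower limit of PI's AUC exceeds 0.5 in 24–91% of studies, and in 62% in the tabulated example. In 61% of that example's studies this occurs together with the index beating every item.
- PI AUC 0.75 beside ETCO₂ AUC 0.76 at correlation 0.5, where PI does add something: the De Long comparison finds PI superior in only 2%. It therefore gives no help in telling a contributing moderate PI from a redundant one.

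**The case against.** The sentence at issue is an expectation, not a test or a decision rule. The endpoint itself only determines a ROC curve. The Background asks for a panel because no ETCO₂ value alone suffices, and index against each item is the matching comparison. No section claims added value of PI over ETCO₂ plus rhythm. All of this stands. A reader might infer that the protocol fixes a wrong benchmark for success; it does not.

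A reader might also infer that nothing in the plan separates a useless PI from an excellent one. That is wrong too: the primary endpoint and the PI-versus-ETCO₂ comparison do so, as shown above. The similar index results at the two extremes also partly reflect a ceiling, since an index can hardly beat a component whose AUC is 0.965.

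It can further be said that the reference model belongs in a separate SAP. That has some force. But the protocol contains its own analysis section, and the single comparison that it states anywhere for this endpoint cannot answer the question that a study of PI raises. Finally, the 89–99% figure depends on a numerical reading of same-data AUCs; under De Long the share is much lower. The size of the problem therefore depends on how the result is read, but its logic does not.

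**Conclusion.** The point holds in a narrow form. Beating each single item cannot show that PI adds to ETCO₂ plus rhythm, and no planned analysis makes that comparison. The gap matters for a moderate PI that overlaps with ETCO₂, not for a PI that is noise or excellent.

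The percentages rest on assumed ETCO₂ and rhythm performance and on one row per patient; the protocol's analysis by 2-minute cycle was not simulated. The structural argument does not depend on those inputs. It affects the interpretation of one secondary endpoint and leaves the primary endpoint and the sizes of 87 and 92 untouched. It is a cheap improvement, not an error that undermines the study.

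**What to change.** In the Statistical Analysis Plan section of the protocol:

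- Fit ETCO₂ + rhythm without PI as the reference for the combined index.
- Test PI's added value by the model with versus without PI: a likelihood-ratio test with one row per patient, or patient-clustered inference if 2-minute cycles are the unit.
- Report both AUCs and their difference with confidence intervals. If the index is fitted and scored on the same cohort, correct for optimism by resampling whole patients. In a bootstrap check, redundant PI showed an apparent AUC gain of +0.006 that became −0.006 after correction, matching −0.006 in new patients.
- Do not use a plain De Long test for this nested same-data comparison. With useless PI it rejects in 0–0.2%, and its power is 4% where the likelihood-ratio test has 53% (PI AUC 0.75, correlation 0.5).
- Keep the single-item comparisons as the panel-versus-single-tool result. The sponsor's expectation need not be reworded.

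The cost is a few lines of text and code on data already collected. There are two downsides. The reported index AUC falls by about 0.02–0.04 after optimism correction. Power is also limited: with ETCO₂ AUC 0.76 and rhythm 50% vs 20%, it is 95% at PI AUC 0.75 if PI is independent of ETCO₂, but about 50% at correlation 0.5 (86% at PI AUC 0.80), and lower if ETCO₂ is stronger. A non-significant result should therefore be reported with its interval and not read as proof that PI adds nothing.

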Perfusion index (PI) is an assessment of the pulsatile strength at a specific monitoring site, and as such PI is an indirect and noninvasive measure of peripheral perfusion. It is calculated by means of pulse oximetry by expressing the pulsatile signal as a percentage of the nonpulsatile signal, both of which are derived from the amount of infrared (940 nm) light absorbed. The PI value is relative to a particular monitoring site, (e.g. the fingertip or toe), of each patient as physiological conditions vary between monitoring sites and individual patients.

Potential Benefits and Risks to Patients:

No foreseeable benefit can be expected on included patients.

Given the observational design and the well studied effects of continuous non-invasive infrared pulse oximetry monitoring we can reliably declare that we expect no possible harm to the patients included in the study.

Methods:

Study Design.

Double-blind study involving ninety two subjects treated with advanced life support according to the European Resuscitation Council (ERC) recommendations will be included in one observatory arms. Patient treatment during resuscitation will be determined by the treating clinician within the frame of ERC recommendations. Monitoring of perfusion index will be initiated as soon as possible and recorded until the end of the resuscitation efforts. ETCO₂ will be placed as soon as possible and recorded until the end of the resuscitation irrespectively if measured while the patient is ventilated through a bag-valve-mask or through a advanced infraglottic airway.

Study population and selection criteria.

All aspects of the study and consent forms will be approved by our Ethical Board prior to implementation. All patients in cardiac arrest, after application of the inclusion and exclusion criteria, with an indication to initiate an advanced life support will be included in the study. Included participants that will be successfully reanimated and that will regain a sufficient level of consciousness will be required to sign a full informed consent.

Inclusion criteria will be a cardiac arrest in a subject aged between 12 to 99 years old with an indication to start an ALS.

Subjects will be excluded from the study if younger than 12 years old, if pregnant or if prisoners at study inclusion.

We aim to recruit 90 patients in cardiac arrest for whom an ALS has been initiated.

Recruitment methods.

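### Withdrawal for clinician non-compliance, and an inclusion criterion that depends on compliance and data during the arrest, let patients be selected once ROSC can be known

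*Protocol*

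**What the plan says.** Three parts of the protocol bear on who ends up in the accuracy estimates.

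- **Withdrawal.** Reasons for Withdrawal or Termination includes "The treating clinician is not compliant with study or ERC procedures" and "Mechanical – technical failure of the monitor". The next section, on handling withdrawals, confirms that patients "may be withdrawn according to the abovementioned pre-specified cases". It adds that "subject withdrawal should be avoided as much as reasonably possible". It sets no time limit for these grounds and does not ask that the decision be made without knowledge of ROSC.
- **Inclusion.** Main Inclusion Criteria in the Study Summary couples consent with "compliance with all aspects of the study protocol, methods, providing data during the cardiac arrest management". Study population and selection criteria, in the Methods, restates inclusion as age plus an indication to start advanced life support. It says that all eligible patients "with an indication to initiate an advanced life support will be included in the study".
- **Data window and dropout.** Under Data collection and reporting, "Data will be collected throughout the intervention up until death or hospital admission or intensive care admission whichever comes first". Sample Size Calculations raises 87 patients to 92 for a possible 5% dropout.

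**The concern.** ROSC is observed during the resuscitation itself. Whether the clinician kept to study or guideline procedures, and whether usable data were produced, can be judged only during or after that resuscitation. A rule that drops patients on either ground can therefore be applied by someone who already knows the outcome.

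If it is applied, the primary sensitivity and specificity no longer describe the arrests that the Methods say will be included. They describe the compliant arrests that yielded data. The Background gives the purpose of prognostication as informing decisions to stop resuscitation or to transport. For that use the important error is a patient who achieves ROSC despite a poor PI result, and a discretionary exit could remove such a patient from the count.

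The two inclusion texts add to the problem. A patient with an indication for advanced life support but no PI data is included under the Methods and can be treated as never included under the Study Summary.

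**Working it through.** **1. The protocol's own figures.** Inputs from Sample Size Calculations: sensitivity and specificity 0.90, ROSC prevalence 0.40, precision 0.10, type I error 0.05 (taken as two-sided, z = 1.96).

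- ROSC patients needed: 1.96² × 0.90 × 0.10 / 0.10² = 34.6.
- Total needed: 34.6 / 0.40 = 86.4, rounded up to 87.
- With 5% dropout: 87 / 0.95 = 91.6, rounded up to 92.

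Both stated figures reproduce, and neither is disputed. The 92 is built so that 87 remain after losses (92 × 0.95 = 87.4). This implies that dropouts are not expected to count towards the 87.

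**2. The texts side by side.**

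| Patient | Methods | Study Summary and withdrawal list |
|---|---|---|
| Eligible, indication for advanced life support, clinician departed from procedures | Included | Can fail the compliance criterion, or be withdrawn |
| Eligible, indication for advanced life support, no data during the arrest | Included | Can fail the data criterion |

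In both rows, the deciding fact arises after resuscitation has begun.

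**3. What one exit does (illustration only).** Take 92 patients, one PI threshold, one result per patient, and the protocol's 90% and 40%.

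- ROSC: 0.40 × 92 = 36.8, with 0.90 × 36.8 = 33.12 true positives.
- Non-ROSC: 92 − 36.8 = 55.2, with 0.90 × 55.2 = 49.68 true negatives.
- One false negative removed: 33.12 / 35.8 = 0.925, so sensitivity goes from 90.0% to 92.5%.
- One false positive removed: 49.68 / 54.2 = 0.917, so specificity goes from 90.0% to 91.7%.

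In whole patients the shift in sensitivity is the same: 33/37 = 89.2% becomes 33/36 = 91.7%.

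**4. Limit of the illustration.** The Primary Endpoint section tests each two-minute PI average against ROSC in the following cycle. There, withdrawing a patient removes all of that patient's cycles. The protocol gives no cycle counts, so the shift on that scale cannot be computed.

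**The case against.** The strongest reply is that no sentence says withdrawn patients' data are discarded. The list is framed as reasons for stopping a study treatment, it governs participation, and analysis sets are commonly left to an SAP. The 5% allowance could equally reflect consent withdrawal or recordings that never started. The compliance criterion may be stock wording attached to consent. The protocol discourages withdrawal, commits to including all eligible patients and calls itself double-blind. One exit moves sensitivity by 2.5 points, a quarter of the planned 10-point precision, and only if that patient happens to be a false negative.

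Much of this stands. Removal from the analysis is an inference, and the size is modest or unknown. However, the point is not that an analysis-set definition is missing. The protocol itself states an inclusion criterion and a withdrawal ground that depend on conduct after the arrest begins, and an SAP cannot recover patients who were never counted as included. The advice to avoid withdrawals is not a rule. The double-blind label does not say who is blinded to what, so it is at most a partial safeguard.

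A reader might also infer that the monitor clause removes patients with an absent or low signal and so inflates sensitivity by several points. The documents do not support this. On plain reading the clause means equipment failure. Under Product Description, "Perfusion index (PI) is an assessment of the pulsatile strength at a specific monitoring site", so a low PI is a test value and not a fault. No failure rate is given. If one assumes that 5% of 92 patients (4.6) have no signal and counts them as test-negative, sensitivity would be 0.90 × (36.8 − 4.6s) / 36.8, where s is their ROSC share. That is 90.0% at s = 0 and 85.5% at s = 0.40. If an absent signal goes with low flow, itself an inference, the small end is more likely. These figures size the sensitivity analysis proposed below; they are not evidence of bias in the plan.

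**Conclusion.** The concern holds in a limited form. The protocol allows withdrawal for clinician non-compliance with no safeguard against knowing ROSC. It also has two inclusion texts that disagree on whether compliance and data during the arrest are required. If these rules are followed and withdrawn patients leave the analysis, as the dropout allowance implies, the primary estimates describe compliant arrests with data and not all eligible arrests.

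The size cannot be derived, because the protocol gives no rate of non-compliance or missing data. The one-patient shifts (sensitivity +2.5 points, specificity +1.7 points) assume one result per patient, one threshold, the protocol's 90% and 40%, and an excluded patient who was misclassified. Nothing shows that exits will be used selectively, and the direction of any bias is not established. This is worth correcting before enrolment, but it does not undermine the design.

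**What to change.** - Reconcile the Study Summary and Methods criteria so that inclusion does not depend on compliance or data provision during the arrest.
- State that clinician non-compliance is not a ground for leaving the primary analysis. A compliant-only analysis can be added as a sensitivity analysis if wanted.
- State that the monitor clause covers equipment faults only, so that an absent or low PI signal does not remove a patient.
- Record the reason for each missing PI reading, and report missing PI by reason and ROSC status.
- Add one sensitivity analysis that counts absent signal as test-negative, with pure equipment faults treated as missing. Test-negative is one convention among several, so it belongs in a sensitivity analysis and not in the primary one.

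The cost is wording, one extra data field and one extra analysis, in which sensitivity may look slightly lower. The field should exist before enrolment starts, because reasons for signal loss are hard to reconstruct later.

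### The per-cycle analysis takes several two-minute PI values from each patient without stating any allowance for clustering; if cycles are pooled under independence methods, the specificity interval is too narrow

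*Protocol*

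**What the plan says.** The Study Summary gives the primary endpoint as "Sensibility and specificity of the perfusion index in predicting a return of spontaneous circulation (ROSC". Under Statistical Analysis Plan, Primary Endpoint, the protocol promises: "We will calculate the sensitivity and specificity at multiple different PI thresholds along with corresponding 95% confidence intervals". It then averages PI over two minutes and continues: "Each value will be tested for its ability to predict ROSC during the following ALS cycle (2 minutes".

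Three other places bear on how many values a patient supplies and how alike they are:

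- Methods, Study Design: "Monitoring of perfusion index will be initiated as soon as possible and recorded until the end of the resuscitation efforts".
- Primary Endpoint, on the change in PI, which is taken "between initial PI and PI values of the cycle preceding ROSC or the last cycle in the absence of ROSC". This presupposes more than one cycle per patient.
- Product Description, which makes PI relative to the monitoring site "of each patient as physiological conditions vary between monitoring sites and individual patients".

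The Secondary Endpoints paragraph first covers initial and final values of PI and ETCO₂, then adds: "Moreover averaged values per 2 min cycle will be assessed for their ability to predict ROSC in the following cycle". It names DeLong's method for comparing the resulting curves. The Tertiary Endpoints paragraph repeats the two-minute design for re-arrest. No section mentions clustering, repeated measures, robust variance or a patient-level bootstrap.

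**The concern.** Sensitivity and specificity computed over cycles have the cycle as denominator, while the independent unit is the patient. A patient who reaches ROSC normally gives one positive cycle, the one just before ROSC. All earlier cycles, and every cycle of a patient without ROSC, are negative. The repeats therefore fall almost wholly on specificity, which is half of the primary endpoint.

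The protocol's own remark that PI levels differ between patients gives a reason to expect positive correlation between one patient's cycles, though not its size. A standard binomial interval over pooled cycles would then be too narrow. Ordinary DeLong also assumes independent observations, so the per-cycle comparison of PI with ETCO₂ has the same gap. What is at stake is the stated precision of specificity and, in some settings, the error rate of the superiority comparison. The point estimates are not in question.

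**Working it through.** **1. The plan's own figure.** Inputs from Sample Size Calculations: sensitivity and specificity 90%, ROSC prevalence 40%, precision 10 points, type I error 0.05.

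- 1.96² × 0.9 × 0.1 / 0.1² = 34.57.
- Sensitivity: 34.57 / 0.40 = 86.4, so 87. Specificity: 34.57 / 0.60 = 57.6, so 58. The larger is the stated 87, and 87 / 0.95 = 91.6 gives 92.

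The figure reproduces with one observation per patient. On that unit the half-width at 87 patients is 1.96 × √(0.09 / 34.8) = 10.0 points for sensitivity and 1.96 × √(0.09 / 52.2) = 8.1 points for specificity.

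**2. What pooling does to the count.** Take about 35 ROSC and 52 non-ROSC patients with m cycles each. Negative cycles: N = 35(m − 1) + 52m, so 226 at m = 3, 400 at m = 5 and 835 at m = 10. Positive cycles stay at 35, one per ROSC patient. The naive specificity half-width, 1.96 × √(0.09 / N), is 3.9, 2.9 and 2.0 points.

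**3. Design effect.** DEFF = 1 + (N/87 − 1) × ICC, with the ICC on the binary test result; coverage of the naive interval = 2Φ(1.96/√DEFF) − 1. With an assumed ICC of 0.3:

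- m = 5: DEFF = 1 + 3.6 × 0.3 = 2.08; half-width 2.9 × √2.08 = 4.2 points; coverage 83%.
- m = 10: DEFF = 1 + 8.6 × 0.3 = 3.58; half-width 2.0 × √3.58 = 3.8 to 3.9 points; coverage 70%.

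A beta-binomial simulation (20,000 runs) gives 82% and 69% for the naive interval, against 93% for a cluster-robust one in both.

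**4. Range over assumptions.** Simulation of 2,500 trials per scenario: 87 patients, 40% ROSC, specificity 0.90, cycles uniform from 1 to 2m − 1 (mean m). Correlation is on the PI scale; 0.1, 0.3, 0.5, 0.7 and 0.9 correspond to 0.04, 0.13, 0.25, 0.41 and 0.65 on the binary result. Entries are true SE / naive SE, then coverage of a nominal 95% Wilson interval, with correlation constant across cycles:

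| Mean cycles | 0.1 | 0.3 | 0.5 | 0.7 | 0.9 |
|---|---|---|---|---|---|
| 3 | 1.05, 93.7% | 1.20, 91.0% | 1.30, 87.1% | 1.42, 83.8% | 1.62, 77.2% |
| 5 | 1.07, 92.8% | 1.27, 87.8% | 1.48, 81.8% | 1.75, 73.9% | 2.03, 66.3% |
| 8 | 1.19, 90.7% | 1.45, 82.6% | 1.76, 73.5% | 2.22, 62.7% | 2.57, 56.0% |
| 11 | 1.26, 87.8% | 1.62, 77.3% | 2.01, 66.5% | 2.46, 58.8% | 3.12, 45.6% |

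If correlation decays from cycle to cycle (lag-1 value 0.1 to 0.9), the ratio is 1.03 to 2.36 and coverage 94.6% down to 58.9%. At lag-1 0.5, coverage is 88.9%, 87.4%, 86.7% and 86.4% for 3, 5, 8 and 11 cycles.

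Middle case (8 cycles, 0.5), naive half-width 2.3 points: 2.3 × 1.76 = 4.0 with constant and 2.3 × 1.29 = 3.0 with decaying correlation. Over all cases the true half-width is 2.0 to 6.3 points. The sensitivity half-width stays at 9.8 to 10.3 points throughout.

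**5. DeLong on per-cycle values.** Under an equal-variance binormal model, 90% sensitivity with 90% specificity implies AUC = Φ(√2 × 1.2816) = Φ(1.812) = 0.965. With equal true AUCs, an assumed correlation of 0.4 between PI and ETCO₂ and the same grid (2,000 trials), type I error at a nominal 0.05 is:

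- AUC 0.965: 0.040 to 0.117 with ordinary DeLong; 0.035 to 0.054 with the clustered version.
- AUC 0.80: 0.040 to 0.065 with ordinary DeLong; 0.045 to 0.064 with the clustered version.

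The upper values at AUC 0.965 arise when within-patient correlation is high.

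**6. The remedy.** For specificity, a percentile bootstrap of whole patients covers 90.6% to 94.7%, and a cluster-robust interval 90.9% to 94.9%.

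**The case against.** The strongest reply is that this is an omission. The protocol neither says that cycles are pooled nor names an interval method, and a separate analysis plan, not at hand, may settle both. The harm needs two unstated choices together: pooling, and an independence interval. The sentence promising intervals comes before the per-cycle sentence, and the only unit quantified anywhere is the patient. If each cycle number were analysed separately, with one value per patient, there would be no clustering. The size rests wholly on assumed cycle counts and correlation. Constant correlation of 0.9 also sits poorly with a study that expects PI to change during resuscitation, so decay is the more plausible pattern. Finally, no specificity threshold is set that a narrow interval could wrongly pass.

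Much of this stands, and it keeps the point conditional and small. It does not remove it. The protocol has its own Statistical Analysis Plan section, which makes each two-minute value a test, promises intervals and names DeLong for curves that include per-cycle values. Because per-cycle values are listed in addition to initial and final ones, pooling is the natural reading. Even with decaying correlation the middle case covers 87%.

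A reader might go further in three ways that the documents do not support:

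- **That 92 patients are too few.** The calculation is per patient and reproduces, and the clustered specificity half-width stays inside 10 points in every case computed.
- **That the reported intervals will cover below 50%.** That needs 11 cycles with constant correlation 0.9; at 3 cycles and 0.1 the effect is negligible.
- **That the re-arrest intervals are shown to be wrong.** The Study Summary lists "Sensibility and specificity of the perfusion index in predicting further arrest following an initial ROSC" and the Tertiary Endpoints paragraph promises an AUC, but neither promises an interval.

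**Conclusion.** The point holds conditionally and is minor. The plan fixes a repeated unit within patients and states no allowance for it. If cycles are pooled and treated as independent, the specificity interval overstates precision. The size depends on quantities the documents do not give: over 3 to 11 cycles and PI-scale correlation 0.1 to 0.9, coverage falls from about 94% to below 50%, with about 74% (constant) or 87% (decaying) in the middle case. Ordinary DeLong on per-cycle values is near nominal in most cases, but it cannot be called safe throughout: at the AUC implied by the planning assumptions, its type I error can reach about 0.10 to 0.12 under high correlation. The point estimates, sample size, sensitivity interval, regression on the change in PI, and initial- and final-value analyses are essentially unaffected.

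**What to change.** In the Statistical Analysis Plan section, state the unit of the per-cycle analysis.

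- **If cycles are pooled:** compute the 95% intervals for sensitivity, specificity and AUC, and the per-cycle AUC difference between PI and ETCO₂, with the patient as cluster. Use a bootstrap that resamples whole patients, or robust variance with the clustered extension of DeLong. Keep plain DeLong for the initial and final values, and apply the same clustering rule to any interval reported for re-arrest.
- **If each cycle number is analysed on its own:** say so; no cluster correction is then needed.

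The cost is one or two sentences and a few lines of code, with no new data and no change in sample size. Specificity intervals become somewhat wider, from about 2.3 to 3.0–4.0 points of half-width in the middle case. The bootstrap brings coverage to about 91–95%, so it does not restore exactly 95% everywhere.
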